### 4.3. Other Endpoints

- Total ischemia and cross-clamp times
- Duration of initial post-transplant invasive mechanical ventilation
- Length of initial post-transplant ICU stay
- Length of initial post-transplant hospital stay
- PGD Scores at T0, T24, T48, and T72 hours post-transplantation
- Incidence of BOS at 6, 12, 24, and 36 months post-transplantation (including post-market follow-up)
- All-cause mortality at 6, 12, 24, and 36 months post-transplantation (including post-market follow-up)
- Lung graft-related mortality at 6, 12, 24, and 36 months post-transplantation (including post-market follow-up).

#### **4.4. Primary Safety Endpoint**

The primary safety endpoint is the number of lung graft-related serious adverse events through the 30-day follow-up or until initial hospital admission (if longer than 30 days) after transplantation per subject. This endpoint is defined to consist of the following serious adverse events (at most one per type):

- Biopsy proven moderate or severe acute rejection
- Respiratory failure requiring prolonged intubation or reintubation
- Bronchial anastomotic complications
- Major pulmonary-related infection.

A more complete description is provided in Appendix 3 of the Protocol.

### **5. STATISTICAL CONSIDERATIONS**

#### **5.1. General Methodology**

All statistical analyses will be performed and all tables and listings will be produced using SAS® Version 9.4 or higher.

The study was designed for 90 transplanted recipients in the U.S. and world-wide (Europe, Australia and Canada).

Continuous variables will be summarized using descriptive statistics, specifically the mean, median, standard deviation, minimum and maximum. Categorical variables will be summarized using frequencies and percentages. All statistical tests will be performed at the 0.05 significance level, unless otherwise specified in this document.

All data collected will be included in the data listings. Data listings will be sorted either by recipient ID or by donor ID, as appropriate. All date fields will be presented in a format of ddmmmyyyy (e.g., 01Jan2017) in the listings.

#### **5.2. Adjustments for Covariates**

No adjustments for covariates will be made in the statistical analyses.

#### **5.3. Handling of Dropouts and Missing Data**

Missing outcomes, although not expected, will be addressed through multiple imputation so that analyses are based on complete data. The following covariates will be used to impute missing outcomes:

- Donor PaO2/FiO2 ratio at the time of the offer: ( $\leq 300$ ,  $> 300$ )
- Expected cross-clamp time for the second lung: ( $\leq 6$  hours,  $> 6$  hours)
- Donor after cardiac death (DCD donor): (Yes, No)
- Donor Age: ( $< 55$  years,  $\geq 55$  years)
- Recipient Gender: (Male, Female)

- Recipient Age

#### **5.4. Interim Analyses**

No interim analyses will be performed.

#### **5.5. Multiple Comparisons / Multiplicity**

No adjustments for multiple comparisons/multiplicity will be made.

#### **5.6. Examination of Subgroups**

No subgroup analyses are planned.

### **6. ANALYSIS POPULATIONS**

#### **6.1. Transplanted Recipient Population**

The transplanted recipient population will consist of all subjects who are transplanted in the trial. Additional supportive analyses of all effectiveness and safety endpoints will be based on the transplanted recipient population.

#### **6.2. Per-Protocol (PP) Population**

The Per-Protocol (PP) population will consist of all subjects who are transplanted without a major protocol violation. Major protocol violations would be considered:

- Ineligible for the study according to the recipient inclusion and exclusion criteria
- Ineligible for the study according to the donor organ inclusion and exclusion criteria
- Failure to complete adequate post-transplant assessments to support the primary effectiveness and primary safety endpoints
- Failure to follow the IFU for the OCS™ Lung System
- Failure to meet Donor Lung Acceptance for Transplantation after assessment on the OCS™ Lung System, as outlined in Section 6.5 of the Protocol.

The primary analysis of all effectiveness endpoints will be based on the PP population, which is appropriate given that the comparator rate is derived from the Control arm of the PP population from the INSPIRE trial. Supportive analyses will be conducted using the Transplanted Recipient population.

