1.4.3. OCSTTM Lung System Testing - INSPIRE

The INSPIRE trial is a randomized, controlled clinical trial comparing outcomes in patients who receive donor lungs meeting the standard criteria for donation preserved using either OCSTTM Lung System or a standard cold preservation solution. The INSPIRE study included 320 subjects at 21 investigational sites in the U.S., Canada, Australia and the European Union and was conducted under IDE [REDACTED], approved on October 26, 2011. The primary objective of the INSPIRE study was to compare the safety and effectiveness of the OCSTTM Lung System with the current cold storage standard of care for the preservation of standard criteria donor lungs. The study was a prospective, multi-center, randomized, controlled investigation with subjects assigned to either the standard cold static organ preservation (control) or to the OCSTTM warm, perfused, and ventilated preservation (treatment).

The primary effectiveness endpoint was a composite of patient survival post-transplantation at day 30, and absence of PGD Grade 3 (PGD3) in the first 72 hours post-transplant (T0 – T72 hours). The OCS Arm and OCS Solution subgroup met the primary effectiveness composite endpoint of all cause patient survival at day 30 and absence of ISHLT PGD3 in the first 72 hours post-transplantation. In addition, the OCS Solution subgroup was statistically superior to the Control arm in the PP population ($p=0.035$), for the pre-specified primary effectiveness endpoint. A sensitivity analysis was performed assessing the same composite of the primary effectiveness endpoint with lung graft-related survival at day 30 and absence of ISHLT PGD3 within the first 72 hours. The OCS Arm and OCS Lung Solution subgroup met the non-inferiority test.

The OCS Arm and OCS Lung Solution subgroup successfully met the primary safety endpoint (i.e., the average number of lung graft-related serious adverse events up to the 30-day follow-up after transplantation), demonstrating non-inferiority test as compared to Control Arm ($p<0.0001$). The SAEs and Lung Graft-Related SAEs and AEs observed in the INSPIRE study are those that are expected for lung transplantation and no safety signals were observed. Long-term (12 and 24 month) results provide further support for the safety of the OCSTTM Lung System.

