9.2.2. Per-Protocol (PP) Population

The Per-Protocol (PP) population will consist of all subjects who are transplanted without a major protocol violation. Major protocol violations would be considered:

- Ineligible for the study according to the recipient inclusion and exclusion criteria
- Ineligible for the study according to the donor organ inclusion and exclusion criteria
- Failure to complete adequate post-transplant assessments to support the primary effectiveness and primary safety endpoints
- Failure to follow the IFU for the OCSTM Lung System
- Failure to meet Donor Lung Acceptance for Transplantation after assessment on the OCSTM Lung System, as outlined in Section 6.5.

The primary analysis of all endpoints will be based on the PP population, which is appropriate given that the comparator rate is derived from the Control arm of the PP population from the INSPIRE trial. Supportive analyses will be conducted using the Transplanted Recipient population.

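### The Per-Protocol survival test excludes recipients for OCS-only reasons that the cold-stored benchmark arm could not have had, which can favour the device

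*SAP*

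**What the plan says.** SAP 6.2 and Protocol 9.2.2 define the PP set as transplanted recipients without a major protocol violation and list five such violations. Two can arise only on the device: "Failure to follow the IFU for the OCS™ Lung System" and "Failure to meet Donor Lung Acceptance for Transplantation after assessment on the OCS™ Lung System". The other three are recipient ineligibility, donor ineligibility and inadequate post-transplant assessment.

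On which set governs, the SAP says: "The primary analysis of all effectiveness endpoints will be based on the PP population". The only reason given is that this is "appropriate given that the comparator rate is derived from the Control arm of the PP population from the INSPIRE trial". The all-transplanted analysis has a secondary role (SAP 6.1): "Additional supportive analyses of all effectiveness and safety endpoints will be based on the transplanted recipient population".

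The benchmark arm is described in the INSPIRE summary (Protocol 1.4.3: "with subjects assigned to either the standard cold static organ preservation (control"). Its survival was 169/180, or 0.939. A margin of 0.12 turns that into the performance goal of 0.819 (SAP 12.1).

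The point is limited to survival. Protocol 9.2.2 makes PP primary for every endpoint ("The primary analysis of all endpoints will be based on the PP population"), but SAP 13.1 runs the safety analyses on the transplanted set.

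**The concern.** Comparing one PP set with another is reasonable only if the same kinds of recipient are removed on both sides. A cold-stored lung cannot breach the OCS instructions or fail an OCS assessment, so whatever the INSPIRE PP rules were, these two reasons removed nobody from the 180. In this trial they act after eligibility and during use of the device under test. Use errors are part of how a device performs in practice.

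The IFU reason also has no severity threshold, and neither document says when PP membership is fixed relative to knowledge of survival. The trial has one unblinded arm (SAP 3.3).

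At stake is the success decision on co-primary #1. If recipients whose preservation run departed from the instructions die more often, taking them out raises the tested survival rate, and the analysis that would show this does not decide success.

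**Working it through.** **Inputs.** One-sided exact binomial test, alpha 0.025, p0 = 0.819, p1 = 0.939, required N 84, planned N 90 (SAP 3.4). The allowance is 90 − 84 = 6 recipients who can leave PP before the required N is lost.

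**Reproducing the plan's figures.** For each n, take the smallest r with P(X ≥ r | n, 0.819) ≤ 0.025. Power is P(X ≥ r | n, 0.939). Power is a sawtooth in n: it first reaches 90% at n=76, and n=84 is the smallest n from which it stays there. The stated 84 is reproduced. The 99% exact interval for 169/180 is also reproduced (87.8% to 97.6%).

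**The death limit does not move.**

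| n | Alive needed | Deaths allowed | Attained alpha | Power at 0.939 |
|---|---|---|---|---|
| 84 | 76 | 8 | 0.0226 | 93.0% |
| 85 | 77 | 8 | 0.0202 | 92.6% |
| 86 | 78 | 8 | 0.0181 | 92.1% |
| 88 | 80 | 8 | 0.0145 | 91.2% |
| 90 | 82 | 8 | 0.0116 | 90.2% |

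The limit is 8 deaths at every n from 84 to 90. A death that leaves with an excluded recipient is therefore no longer counted, and the limit does not tighten to compensate.

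**Sensitivity of the decision** (p = P(X ≥ alive | n, 0.819)):
- 9 deaths: 81/90, p=0.0255, fail. Remove one recipient who died: 81/89, p=0.0130, pass at 0.025.
- 10 deaths: 80/90, p=0.0504, fail. Remove two who died: 80/88, p=0.0145, pass at 0.025.

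These passes are at 0.025. At the Hochberg step of 0.0125, which applies if the utilization test misses 0.025, neither would pass.

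**Type I error in PP.** Assume all-recipient survival is exactly 0.819, 6 of 90 are excluded, and mortality among the excluded is q. Then

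PP survival = (90 × 0.819 − 6 × (1 − q)) / 84, and type I error = P(X ≥ 76 | 84, PP survival).

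| q (assumed) | PP survival | Type I error |
|---|---|---|
| 18.1% (same as overall) | (73.71 − 4.914)/84 = 0.819 | 0.023 |
| 30% | (73.71 − 4.2)/84 = 0.8275 | 0.035 |
| 50% | (73.71 − 3.0)/84 = 0.8418 | 0.070 |
| 100% (extreme) | 73.71/84 = 0.8775 | 0.285 |

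The nominal level is 0.025. With equal mortality there is no inflation above it. If q is below 18.1%, the exclusions work against the device.

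**The case against.** **INSPIRE PP definition.** The documents give the arm and the rate but not the rules. The Control set may have had its own cold-storage exclusions, which would be a natural counterpart to an IFU exclusion. This stands. It does not rescue the plan's argument, because the counterpart is not shown and the plan relies on the PP label alone.

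**Direction.** A reader might infer that the test is tilted toward the device. The documents do not support that. They give neither the number of exclusions expected nor any outcomes for excluded recipients. Worse survival in that group is plausible but assumed.

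**On-device acceptance.** A recipient gets a subject number only once the lungs have met the on-device criteria (Protocol 6.3), and Protocol 6.5 requires those criteria for transplantation. This exclusion should therefore be nearly empty. A reader might also take it to remove borderline lungs. It does not: it removes only lungs that fail, and a narrow pass stays in. The IFU reason carries most of the risk.

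**Size.** It is tempting to size the effect by the chance of passing. With 6 of 90 excluded, assumed mortality of 20% in them and 8% in the rest gives 60% in all recipients against 77% in PP. With 30% and 10% the figures are 29% and 53%. These gaps cannot be put down wholly to the exclusions. With equal mortality of 8% in both groups the figures are already 71% and 77%, and with 10% in both they are 45% and 53%. About 6 of the 17 points and about 9 of the 24 therefore come from the fixed 8-death limit at a smaller n. Nor do all exclusions flip a result: from 80/90, dropping five recipients of whom one died leaves 76/85, p=0.042, still a fail.

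**Already covered.** SAP 12.1 summarises survival in both populations, SAP 7 and 8 report population counts and deviations by type, and the Clinical Events Committee evaluates possible deviations (Protocol 14.4). A discrepancy would be visible, but it would not change the success decision.

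**Conclusion.** The concern holds in a limited form. The primary survival set applies two device-only exclusions that cannot have applied to the cold-stored benchmark, so the stated justification does not make the sets comparable. The exclusions can favour the device; the documents do not show that they do.

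The effect could be decisive near the boundary, where one excluded death can reverse the result. Under a true survival of 0.819 with 6 of 90 excluded, the type I error stays at 0.023 if the excluded die at the overall rate and rises to 0.035 at 30% mortality and 0.070 at 50%. Both the six exclusions and the mortality values are assumptions; six is the number that the step from 84 to 90 can absorb.

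This should be changed before the analysis. It does not show that the trial would reach a wrong conclusion.

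**What to change.** In SAP 6.2 and Protocol 9.2.2, make the existing Transplanted Recipient Population primary for co-primary #1, and report the present PP result as supportive. This is cleaner than building a third population with the two reasons taken out. The Protocol synopsis and SAP 12.1 need matching wording.

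An alternative is to require success in both sets. At 0.025, if PP keeps at least 84 recipients, this asks no more than the all-transplanted test: 8 or fewer deaths among all 90 means 8 or fewer in any subset, and the limit is 8 throughout that range.

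For the PP set that is kept, state in advance what counts as an IFU failure and fix membership without knowledge of survival.

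The cost is wording only, with no added patients or data. With all 90 recipients, success needs at least 82 alive, attained alpha is 0.0116 and power is 90.2% at 0.939. The critical value is the same at the Hochberg level of 0.0125. By comparison, with 84 in PP that level needs 77 alive and gives 86.0% power. The downside is that the reported survival may be slightly less favourable, and the primary set would also include any recipients with eligibility violations.

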### **7. SUBJECT AND DONOR LUNG DISPOSITION**

The numbers of consented subjects, screen failures as defined in section 6.3 of the protocol, subjects in the PP Population, and subjects in the Transplanted Recipient Population will be presented. The display will also present the number and percentage of patients who completed the study, who withdrew from the study early, both overall

and by time period (before Day 30, between Day 30 and 6 months, and between 6 months and 12 months), and the reason for withdrawal.

Donor lung disposition details will be summarized for eligible donor subjects using frequencies and percentages.

## **8. PROTOCOL DEVIATIONS**

Protocol deviations will be summarized by type of deviation and overall using counts and percentages.

## **9. DEMOGRAPHIC AND BASELINE CHARACTERISTICS**

Recipient demographic and baseline characteristics will be summarized for the PP and Transplanted Recipient Populations. Frequencies and percentages will be presented for gender, ethnicity, race, blood type, and type of status (urgent, high-urgent, or LAS). Descriptive statistics will be presented for age, height, weight, and lung allocation score (if type of status is LAS). Recipient height and weight will also be summarized, stratified by gender.

Donor demographics, baseline characteristics, and donor inclusion criteria will be summarized for the donors of the PP and Transplanted Recipient Populations.

Frequencies and percentages will be presented for gender, ethnicity, race, blood type, and donor inclusion criteria. Descriptive statistics will be presented for age, height, and weight.

Indications for transplant, risk factors, and medical history for the recipient at screening will be summarized for the PP and Transplanted Recipient Populations using descriptive statistics for continuous variables and frequencies and percentages for categorical variables.

Donor medical history will be summarized for the donors of the PP and Transplanted Recipient Populations using descriptive statistics for continuous variables and frequencies and percentages for categorical variables.

Donor cause of death (anoxia, cerebrovascular/CNS, head trauma, chest trauma, aspiration, cardiac, or other) and whether the donor experienced cardiac arrest will be summarized for the donors of the PP and Transplanted Recipient Populations using frequencies and percentages.

Findings from the final donor bronchoscopy prior to retrieval, the inspection and palpation of lungs in the donor's chest, and donor lung imaging will be summarized for the donors of the PP and Transplanted Recipient Populations using frequencies and percentages.

Final donor arterial blood gas (ABG) (PaO2, FiO2, PEEP, and the PaO2/FiO2 ratio) test results, at the time of lung offer, will be summarized for the donors of the PP and Transplanted Recipient Populations using descriptive statistics.

## **10. DONOR OPERATIVE CHARACTERISTICS AND OCS BLOOD GASES AT THE TIME OF ACCEPTANCE BEFORE TRANSPLANT**

Donor operative characteristics will be summarized using descriptive statistics for continuous variables and frequencies and percentages for categorical variables.

OCS blood gas (PaO2, FiO2, PEEP, and the PaO2/FiO2 ratio) test results will be summarized by timepoint (initial and final assessments on the OCS Lung System) using descriptive statistics.

These analyses will be performed for the donors lungs of the PP and Transplanted Recipient Populations.

## **11. TRANSPLANT CHARACTERISTICS AND RECIPIENT POST-TRANSPLANT ICU STAY**

Transplant characteristics will be presented using descriptive statistics for continuous variables and frequencies and percentages for categorical variables.

ICU stay will be presented using descriptive statistics for the initial ICU stay duration, the re-admission ICU stay duration from ICU arrival to clinical order of discharge, and the re-admission ICU stay duration from ICU arrival to actual discharge, and frequencies and percentages for whether the recipient was readmitted to the ICU (during the first 30 days post transplant or initial hospital discharge, whichever occurs later) per Appendix 4 of the protocol.

These analyses will be performed for the PP and Transplanted Recipient Populations.

## **12. ANALYSIS OF EFFECTIVENESS ENDPOINTS**

### **12.1. Co-Primary Effectiveness Endpoint #1**

The first co-primary hypothesis is that the proportion of transplanted recipients of lungs preserved using the OCS™ Lung System surviving at Day 30 and at initial hospital discharge post-transplantation (whichever occurs later) is greater than a performance goal based on the corresponding proportion of patients in the Per-Protocol population of the Control arm of the INSPIRE trial (0.939) with a margin of 0.12 (12%).

The determination of the margin (12%) is based on the following:

- The estimate observed in the Control arm of the INSPIRE trial [93.9% (169/180)] serves as the target for the first co-primary endpoint.
- The 99% exact binomial confidence interval around the INSPIRE outcome (87.8% to 97.6%) provides an indication of conservative variability for eligible organs under standard of care with a lower bound about 6% away from the target.

- The lack of historical data and limited knowledge with respect to non-ideal donor lung transplantation suggests a 12% margin (i.e., doubling the lower bound distance of 6% associated with the INSPIRE estimate).

The formal statistical hypothesis test is as follows:

$$H_{01}: \pi_{OCS\ Lung} \leq 0.819$$

$$H_{11}: \pi_{OCS\ Lung} > 0.819$$

where  $\pi_{OCS\ Lung}$  is the proportion of transplanted recipients alive Day 30 and at initial hospital discharge.

This co-primary effectiveness endpoint will be summarized for the PP and Transplanted Recipient Populations using a count and percentage with an exact 95% confidence interval for the percentage based on the binomial distribution. A one-sided exact binomial test at the 0.025 significance level will be performed to test the null hypothesis,  $H_{01}$ .

## 12.2. Co-Primary Effectiveness Endpoint #2

The second co-primary hypothesis is that the Utilization Rate (defined in Section 4.1 above) is greater than a performance goal of 0.54 (54%), which is based on the utilization rate reported for XVIVO in the NOVEL Trial. The formal statistical hypothesis test is as follows:

$$H_{02}: \pi_{OCS\ Lung} \leq 0.54$$

$$H_{12}: \pi_{OCS\ Lung} > 0.54$$

where  $\pi_{OCS\ Lung}$  is the observed utilization rate in the EXPAND trial.

The appropriateness of the performance goal of 54% is based on the following:

- The 54% rate is the only published data available on utilization rate for non-ideal donor lungs.
- The donor lung inclusion/exclusion criteria are similar to those used for the XVIVO NOVEL study. Where differences exist, they tend to make the donor lungs more challenging for EXPAND II vs NOVEL. For example:
  - EXPAND II will enroll DCD donors with any  $\text{PaO}_2/\text{FiO}_2$  ratio, while the NOVEL study only included DCD donors with  $\text{PaO}_2/\text{FiO}_2$  ratio  $\geq 300$  mmHg.
  - EXPAND II will include older donors (age  $> 55$  years) while NOVEL did not have an inclusion criterion based on donor age. Donor age  $> 55$  years old is known to have a negative impact on outcomes after lung transplantation.
- Finally, this co-primary endpoint is designed to show superiority of the OCS™ Lung System to the XVIVO EVLP device. Demonstrating superiority to the only published data on utilization in the non-ideal donor lung population is a rigorous and appropriate test of a new technology.

This co-primary effectiveness endpoints will be summarized for the PP and Transplanted Recipient Populations using a count and percentage with an exact (Clopper-Pearson) 95% confidence interval for the true percentage based on the binomial distribution. A one-sided exact binomial test at the 0.025 significance level will be performed to test the null hypothesis,  $H_{02}$ .

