9.3.2. Co-primary Effectiveness Endpoint #2

The second co-primary hypothesis is that the Utilization Rate (defined in Section 4.1 above) is greater than a performance goal of 0.54 (54%), which is based on the utilization rate reported for XVIVO in the NOVEL Trial.² The formal statistical hypothesis test is as follows:

$$H_0: \pi_{OCS\ Lung} \leq 0.54$$

$$H_1: \pi_{OCS\ Lung} > 0.54$$

where $\pi_{OCS\ Lung}$ is the observed utilization rate in the EXPAND trial.

The appropriateness of the performance goal of 54% is based on the following:

- The 54% rate is the only published data available on utilization rate for non-ideal donor lungs.⁵⁶
- The donor lung inclusion/exclusion criteria are similar to those used for the XVIVO NOVEL study. Where differences exist, they tend to make the donor lungs more challenging for EXPAND II vs NOVEL. For example:
 - EXPAND II will enroll DCD donors with any $\text{PaO}_2/\text{FiO}_2$ ratio, while the NOVEL study only included DCD donors with $\text{PaO}_2/\text{FiO}_2$ ratio ≥ 300 mmHg.
 - EXPAND II will include older donors (age > 55 years) while NOVEL did not have an inclusion criterion based on donor age. Donor age > 55 years old is known to have a negative impact on outcomes after lung transplantation.⁴
- Finally, this co-primary endpoint is designed to show superiority of the OCSTM Lung System to the XVIVO EVLP device. Demonstrating superiority to the only published data on utilization in the non-ideal donor lung population is a rigorous and appropriate test of a new technology.

This co-primary effectiveness endpoint will be summarized using a count and percentage with an exact 95% confidence interval for the true percentage based on the binomial distribution. A one-sided exact binomial test at the 0.025 significance level will be performed to test the null hypothesis, H_0 .

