## 3. STUDY DESIGN

### 3.1. Overview

This is a prospective, pivotal, international, single-arm trial of donor lungs and donor lung transplant recipients.

The proposed clinical trial seeks to evaluate the safety and effectiveness of the OCS™ Lung System for donor lungs that today may not be transplanted due to the limitations associated with cold storage technique (such as ischemia and the inability to evaluate organ function following cold preservation). The results of the OCS™ Lung System with non-ideal donor lungs in this study will be compared to the results for both the control arm of the INSPIRE trial and to the results of the NOVEL study of the XEVIVO EVLP system.

Subjects will be followed for up to 36 months from the date of transplantation. The details of the follow-up are summarized in Appendix 4 of the Protocol as follows:

- All subjects will be followed from transplant to discharge.
- Patient survival will be documented on Day 30 post-transplant and at initial hospital discharge following transplantation (if longer than 30 days).
- Patient survival and clinical diagnosis of BOS will be documented at 6, 12, 24, and 36 months patient follow-up (these are post-market follow-up timepoints) per Appendix 4 of the Protocol.

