### **3.2. Method of Assigning Subjects to Treatment**

Not applicable.

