### **3.4. Determination of Sample Size**

The sample size for this trial was determined based on providing adequate statistical power for hypothesis testing of the two co-primary effectiveness endpoints. All sample size calculations were performed using PROC POWER in SAS.

For the first co-primary endpoint, the calculations assumed a one-sided exact binomial test, an alpha level of 0.025, a control-based rate of 0.939 with a margin of 0.12 (to derive the performance goal of 0.819), a true survival rate for OCS™ of 0.939, and desired power of 90%. Based on these specifications, the required sample size was determined to be 84 transplanted recipients.

For the second co-primary endpoint, the calculations assumed a one-sided exact binomial test, an alpha level of 0.025, a performance goal of 0.54, a utilization rate of 72% for OCS™, and desired 90% power. Based on these specifications, the required sample size was determined to be 84 transplanted recipients

In order to ensure that a sufficient number of subjects are evaluable in the per-protocol population of the trial, 90 transplanted recipients in the study are expected to provide adequate power to evaluate the two co-primary effectiveness objectives given the assumptions described.

Due to multiple primary endpoints, the Hochberg Method will be used to control familywise error. The p-values for each of the co-primary endpoints will be ordered from highest to lowest. If the highest p-value is less than 0.025 then both endpoints achieve statistical significance and the null hypothesis of each co-primary endpoint can be rejected. If not, then the lower of the two p-values will be assessed against a significance level of 0.0125. If the adjusted significance level of 0.0125 is applied to any of the co-primary endpoints, the power of that analysis will be greater than 85%. Therefore, the study will be considered successful in either of the two scenarios described above.

With regard to the primary safety endpoint, the pre-specified safety margin of 0.7 events per patient, the estimated mean of 0.29 events per patient (with an estimated standard deviation of 2.0), a one-sided alpha of 0.025, and the sample size of 90 transplanted recipients results in power greater than 90% when considering a one-sample t-test on the mean.

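### Co-primary endpoint #2 is described as showing superiority to another device, but a single-arm test against a fixed 54% can show only that utilization exceeds 54%

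*SAP*

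**What the plan says.** SAP 3.1 describes a "prospective, pivotal, international, single-arm trial of donor lungs and donor lung transplant recipients". SAP 3.2, on assignment to treatment, reads "Not applicable", and SAP 5.2 rules out covariate adjustment.

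For the second co-primary endpoint, SAP 12.2 sets H0: π ≤ 0.54 against H1: π > 0.54. It calls 0.54 a performance goal, which "is based on the utilization rate reported for XVIVO in the NOVEL Trial". A "one-sided exact binomial test at the 0.025 significance level will be performed". Protocol 9.3.2 sets the same hypotheses and test. The sample size in SAP 3.4 and Protocol 9.7 assumes "a performance goal of 0.54, a utilization rate of 72% for" OCS.

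Both sections then list reasons why 54% is an appropriate goal. The last reason says that "this co-primary endpoint is designed to show superiority of the" OCS Lung System to the XVIVO EVLP device, and adds: "Demonstrating superiority to the only published data on utilization in the non-ideal donor lung population is a rigorous and appropriate test" of a new technology. Neither document gives a count, a denominator or a confidence interval for the 54%.

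**The concern.** The hypothesis contains one unknown, the OCS utilization rate. The other device enters only through the constant 0.54, which is itself a rate observed in another trial. The test therefore controls the chance of a false claim that OCS exceeds 54%. It does not control the chance of a false claim that OCS exceeds the other device's true rate, and it does nothing about differences in donors, sites or period.

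The plan treats its other external benchmark more carefully. For survival, Protocol 9.3.1 and SAP 12.1 give the source count (169/180) and a 99% interval, and use that uncertainty to set the margin. For utilization the benchmark is taken as exact, and a device-level conclusion is attached to it.

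At stake is what a pivotal trial may say. With the sentence left in, a result that just clears the goal could be reported as intended evidence of superiority over a named device.

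**Working it through.** **Inputs.** From SAP 3.4 and 12.2: p0 = 0.54, p1 = 0.72, one-sided alpha 0.025, 90% power, N = 84. The number m of NOVEL lungs behind the 54% is not in the documents. I assume m = 50, 100, 200, 400 and 1000.

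**1. Reproduce the plan's figure.** The pass mark is the smallest r with P(X ≥ r | N, 0.54) ≤ 0.025.
- At N = 84, P(X ≥ 54) = 0.0365 and P(X ≥ 55) = 0.0219. So r = 55, or 55/84 = 65.5%.
- Power is P(X ≥ 55 | 84, 0.72) = 0.925.
- Exact power first reaches 0.90 at N = 76, drops below it at 77, 78, 80 and 83, and stays at or above 0.90 from 84 on. The stated 84 is reproduced.

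**2. Chance of passing if the two devices are truly equal.** Two formulations, both with N = 84:
- (a) Both true rates are 0.54 and the goal is set at the rate y/m observed in m lungs: Σ over y of P(Y = y | m, 0.54) × P(X ≥ r(y/m) | 84, 0.54).
- (b) The goal is fixed at 0.54 with pass mark 55, and the common true rate is uncertain given x0 = 0.54m successes in m: P(X ≥ 55 | 84, p) averaged over Beta(x0 + 0.5, m − x0 + 0.5). This is a predictive probability, not a repeated-sampling error rate.

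**3. Two-sample comparison at the barest pass.** With pooled rate p̄ = (55 + x0)/(84 + m), z = (55/84 − 0.54)/√[p̄(1 − p̄)(1/84 + 1/m)]. For m = 100: p̄ = 109/184 = 0.592, the standard error is 0.0727, z = 0.1148/0.0727 = 1.58 and one-sided p = 0.057. The last column repeats this with an observed 72%, the planned rate.

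| m (assumed) | 2(a) | 2(b) | p at 55/84 | p at 72% |
|---|---|---|---|---|
| 50 | 10.3% | 10.6% | 0.094 | 0.017 |
| 100 | 6.4% | 6.7% | 0.057 | 0.006 |
| 200 | 4.1% | 4.5% | 0.037 | 0.002 |
| 400 | 3.0% | 3.3% | 0.027 | 0.001 |
| 1000 | 2.3% | 2.6% | 0.021 | <0.001 |

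For m from 50 to 400, a bare pass does not reach one-sided 0.025 in a two-sample comparison, whereas an observed 72% does. The excess over the nominal 2.5% shrinks as m grows and is gone by about 1000.

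These figures take 84 as the number of lungs assessed, as the plan's calculation does.

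**The case against.** The strongest reply is that the sentence is only rationale. It is the last bullet in a list defending the choice of 54%. The hypotheses, the exact test, the interval and the success rule in Protocol 9.7 and SAP 3.4 are all written against 0.54, and the Protocol synopsis refers to NOVEL as a benchmark. This stands. A reader might infer that device superiority is the trial's formal success criterion, or that the test or sample size is wrong. The documents support neither: success is rejection of the stated nulls, and 84 is right for them.

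A reader might also infer that the error rate of a superiority claim is well above 2.5%. That depends on a NOVEL denominator the documents do not give. It holds for a small comparator and fails for a large one. At the planned 72%, sampling error in the 54% would not overturn the comparison at any size tabulated.

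Finally, the plan says that donor differences tend to make EXPAND II lungs more challenging, so any bias would work against OCS. That may help to justify 54% as a goal, but the direction is asserted rather than shown. A donor can qualify on expected cross-clamp time or age alone (Protocol 5.1.1). In EXPAND I, 29% of transplanted lungs met the low-ratio criterion, so 71% were not recorded as meeting it. That NOVEL lacked an age inclusion criterion does not show that it had no older donors. Even if the direction is right, the argument does not turn a one-sample test into a comparison of devices.

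**Conclusion.** The point holds as one of interpretation. Protocol 9.3.2 and SAP 12.2 attribute to this endpoint a property that the design lacks. A pass supports the statement that utilization exceeds 54%, and no statement about OCS relative to the other device.

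This conclusion does not depend on NOVEL's size. Only the numerical excess does: from about 10–11% at 50 assumed lungs down to about nominal at 1000. Those figures assume equal true rates and 84 lungs. Any bias from donor mix, sites or period is extra, in a direction and amount that the documents do not allow to be calculated.

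**What to change.** - In Protocol 9.3.2 and SAP 12.2, delete the two superiority sentences. State that success on this endpoint means utilization exceeds a fixed performance goal of 54%, and that no inference on the relative performance of the two devices will be drawn.
- In Protocol 3.1 and SAP 3.1, which say that results will be compared with those of NOVEL, call NOVEL a benchmark, in line with the Protocol synopsis.
- Do not add a cross-trial difference with a confidence interval as a substitute. The documents lack the NOVEL counts, and it would bring back the same unadjusted comparison.

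The cost is wording only. The pass mark of 55/84, alpha, power, sample size and conduct are unchanged. The sponsor gives up a device-superiority claim that this trial cannot support.
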